depression taking chlorpromazine and lithium, both medications known to increase seizure risk. To date, there has been a single report of an induced focal motor seizure during single pulse TMS of an epilepsy patient with a known epileptic focus in the left frontal cortex (Classen et al 1995). These few reported seizures were not associated with long term adverse outcome (Schrader et al. 2004).

In the event of a concurrent seizure during stimulation, one or more co-investigators with specialty training in epilepsy will be present to monitor for adverse effects and monitor for exacerbation of seizure type and frequency. If there is immediate cause for concern the PI and Co-PI will make necessary medical arrangements, including direction to the emergency room if needed. If any other unanticipated adverse events occur which are thought to be related to study intervention, the patient will be withdrawn from further participation in the study. Though our clinical trial will include a safety-monitoring plan, there are no known severe or lasting adverse effects with TMS using proper set-up.

1. Though minimal, due to the concern of potential increased seizures with TMS, we will monitor increase in seizure severity attributable to TMS by identifying all instances of generalized tonic clonic seizures after TMS treatments (defined as occurring within 20 minutes of stimulation). In addition, subjects will be asked to keep a seizure diary for the 7 days prior to stimulation, and the 7 days after stimulation. Instances where seizure frequency increased after TMS will be reported to the IRB within 1 week.
2. If a self-limited, short (<5 min) complex partial seizure or evolution into generalized tonic clonic seizures occur during the procedure, TMS mapping will stop for that day.
3. In case of, pain, transient hearing impairment, the patient's primary epileptologist will be notified and appropriate medical followup will be arranged.
4. If any other unanticipated adverse events occur, the patient will be withdrawn from further participation in the study.

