2.2 Secondary Objective(s)

This trial is also designed to detect safety and tolerability of nTMS in epilepsy patients.

3 Study Design

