3.1.1 Baseline clinical visit and seizure diary

We will enroll 14 patients who will undergo epilepsy surgery with expected subdural grid coverage over primary motor cortex. Potential subjects will be identified at the weekly multi-disciplinary epilepsy conference. Subjects must have a recent (<2 years) MRI scan, and registration of the TMS coil to the MRI scan via the Brainsight neuronavigation system will be utilized to guide TMS coil placement (Gugino et al 2001). When a presurgical fMRI is available which demonstrates the patient's hand knob, the fMRI will be used with the Brainsight neuronavigation system. Subjects will be recruited and consented during a presurgical clinical visit where the patient's primary epileptologist will introduce members of the research team.

Patients will be asked to keep a 7 day seizure diary prior to the TMS session.

3.1.2 nTMS mapping

Patients will receive a session of single-pulse TMS mapping of the motor area, at the outpatient TMS clinic at NYU Neurology Ambulatory Care Center, at [name] prior their epilepsy surgery, according to the following procedures:

- a. Determination of the motor threshold by (1) finding the most excitable region in the hand knob which elicits the strongest compound muscle action potential (CMAP) in the APB muscle; (2) finding the motor threshold by determining output stimulation intensity which generates peak to peak CMAP response above 50 mV in 5/10 stimulation cycles (Rossini et al., 1994).
- b. Concurrent EMG will be measured with electrodes placed at APB, abductor digiti minimi, flexor carpi radialis muscles. Reference electrode will be placed at the ipsilateral elbow above the brachial biceps muscle.
- c. Mapping of the upper extremity. After determination of the MT, mapping of the UE will be performed at 110% of the rMT. All positive and negative stimulation sites will be recorded and saved.

Patients will be closely monitored during TMS stimulation. Each subject will have a complete neurological examined by a neurologist before and immediately after nTMS. Patients will also be provided a side effects questionnaire after TMS mapping. Patients will then be asked to keep a 7 day seizure diary after the nTMS session

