3.3 Secondary Study Endpoints

In addition, this study is designed to detect safety and tolerability of TMS in the epilepsy patient, as measured by 7 day seizure diaries before and after the nTMS sessions.

4 Subject Selection and Withdrawal

We will recruit 14 patients, aged 12-60 years, who will have motor mapping and epilepsy surgery. Because nTMS is expected to most benefit pediatric patients, we plan to enroll at least 4 subjects under the age of 17, to establish validity in this population. There will be no restrictions on race or ethnicity.

Safety and tolerability in healthy volunteers is established for TMS in previous studies, and therefore healthy controls will not be necessary. However side effect questionnaire will be provided after TMS mapping.

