8.1 Definitions

Unanticipated Problems Involving Risk to Subjects or Others

Any incident, experience, or outcome that meets all of the following criteria:

- Unexpected in nature, severity, or frequency (i.e. not described in study-related documents such as the IRB-approved protocol or consent form, the investigators brochure, etc)
- Related or possibly related to participation in the research (i.e. possibly related means there is a reasonable possibility that the incident experience, or outcome may have been caused by the procedures involved in the research)
- Suggests that the research places subjects or others at greater risk of harm (including physical, psychological, economic, or social harm).

Unanticipated Adverse Device Effect

An Unanticipated Device Effect is any serious adverse effect on health or safety, or any life-threatening problem or death caused by, or associated with a device, if that effect, problem, or death was not previously identified in nature, severity, or degree of incidence in the investigational plan or application (including a supplementary plan or application), or any other unanticipated serious problem associated with a device that relates to the rights, safety, or welfare of subjects.

Serious injury

Any injury or illness that is any one of the following:

- life-threatening
- results in permanent impairment of a body function or permanent damage to body structure
- necessitates medical or surgical intervention to preclude permanent impairment of a body function or permanent damage to a body structure

Adverse Event

(a) In parallel with recording the primary outcome, we will monitor for increase in seizure severity attributable to TMS by identifying all instances of generalized tonic clonic seizures after TMS treatments. Instances where seizure frequency increased after TMS will be reported to the IRB within 72 hours.

(b) If a self-limited, short (<5 min) partial seizure or evolution into generalized tonic clonic seizure occur, TMS mapping will stop for that day.

(c) If a secondarily generalized (convulsion starting in one area of body and then spreading to other areas) or 2 partial seizures occur during treatment, the patient will be withdrawn from further participation in the study.

(d) If any other unanticipated adverse events occur, the patient will be withdrawn from further participation in the study.

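### The safety and tolerability endpoint in 3.3 rests on seizure diaries alone: it cannot measure tolerability, does not clearly cover the nTMS session, and has no safety analysis or safety population behind it

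*Combined protocol and SAP*

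**What the plan says.** Section 2.2 states the objective: "This trial is also designed to detect safety and tolerability of nTMS in epilepsy patients". The Study Summary repeats it as a secondary outcome without naming a measure. The only operational definition is in Section 3.3, where safety and tolerability are taken "as measured by 7 day seizure diaries before and after the nTMS sessions".

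The diary windows appear in two other places. Section 1.4.1 says that "subjects will be asked to keep a seizure diary for the 7 days prior to stimulation, and the 7 days after stimulation". Section 3.1.2 says "Patients will then be asked to keep a 7 day seizure diary after the nTMS session", and Section 6.2 likewise starts the second diary after the visit.

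Other safety data are planned outside the endpoint. Section 3.1.2 has a neurologist examine each subject before and immediately after nTMS and adds "Patients will also be provided a side effects questionnaire after TMS mapping". The introduction to Section 4 mentions the questionnaire again: "However side effect questionnaire will be provided after TMS mapping". Section 1.4.1 monitors generalized tonic clonic seizures after TMS, "defined as occurring within 20 minutes of stimulation". Sections 8.2 and 10.1 require adverse device effects and adverse events to be recorded, with severity and relationship scored.

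Section 7.2 describes only the mapping comparison. Section 7.3 defines one analysis population: subjects who finish nTMS mapping and go on to DCS.

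**The concern.** Section 1.4.1 names an induced seizure as the most serious possible side effect. The one case it cites in a patient with epilepsy was a focal motor seizure during single-pulse TMS. An endpoint that compares the week before with the week after looks at the periods around that risk and not clearly at the session itself. It also has no way to register the non-seizure effects that make up most of the side effects listed in the same section.

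At stake is what the trial can report on its second objective. Followed literally, the endpoint could show no change in diary seizures and be presented as evidence of safety and tolerability, while the questionnaire, examination and adverse event data stay outside any planned summary. The patients most affected are also the ones most likely to drop out of the single analysis population.

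**Working it through.** No figure in the plan underlies this endpoint. The sample size in Section 7.1 is set on the mapping comparison only (10 subjects, raised by about one third: 10 × 4/3 = 13.3, so 14). The check is therefore mainly textual, with a short calculation for scale.

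**1. What is recorded against what is in the endpoint.**

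| Harm | Recorded where | In 3.3? | Analysed in 7.2? |
|---|---|---|---|
| Seizure in the week before or after | Diaries (3.1.1, 3.1.2) | Yes | No |
| Seizure during the session | Specialist presence (6.2), adverse event records (8.2, 10.1) | Not clearly | No |
| Generalized tonic clonic seizure within 20 minutes | Monitoring (1.4.1) | Not by name | No |
| Headache, pain, syncope, hearing change | Questionnaire (3.1.2, 6.2), adverse event records | No | No |
| New neurological finding | Examination before and immediately after (3.1.2) | No | No |

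**2. The diary windows.** Section 3.1 gives the session 2 hours. The windows are the 7 days before and the 7 days after, with no clock time and no rule for the session day. Two readings are possible. If the session day is day 1 of the second diary, an in-session seizure can be counted. If the second diary starts once the visit is over, it cannot. Nothing in the document decides between them. Non-seizure effects are missed under both, because a seizure diary does not ask about them.

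**3. The 20-minute monitor.** It covers generalized tonic clonic seizures only. A focal seizure, such as the cited case, would not meet it, and 3.3 does not refer to it.

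**4. Who is analysed.** Sections 1.4.1 and 8.1(b) stop mapping for the day after a short partial seizure or a generalized one. Section 8.1(c) goes further for secondary generalization or if "2 partial seizures occur during treatment, the patient will be withdrawn from further participation in the study". A subject stopped or withdrawn in this way may not finish mapping and would then fail the 7.3 condition. So would a subject who is fully mapped but never has DCS. No separate safety set is defined, and nothing says whether a withdrawn subject still keeps the second diary.

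**5. Scale.** Inputs: n = 14 enrolled and 10 needed (7.1); mild adverse events in about 5% (1.4.1), treated here as an independent per-subject probability, which is an assumption.

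- Expected mild events: 14 × 0.05 = 0.7. For 10 subjects: 10 × 0.05 = 0.5.
- Chance of at least one: 1 − 0.95^14 = 51%. For 10 subjects: 1 − 0.95^10 = 40%.
- In-session seizure, at assumed rates: 1 − 0.99^14 = 13% at 1%, and 1 − 0.999^14 = 1.4% at 0.1%.
- If no event is seen, the one-sided 95% upper bound is 1 − 0.05^(1/14) = 19.3% for 14 subjects, and 1 − 0.05^(1/10) = 25.9% if only 10 remain in the analysis.

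**The case against.** The strongest reply is that in-session harm is well covered. An epilepsy specialist is present, examinations bracket the session, a questionnaire follows it, adverse device effects are followed to resolution or stabilization, and a seizure may prompt a study pause. A convulsion could not pass unnoticed. This stands. A reader might infer from 3.3 that the trial does not observe harm during mapping; Sections 3.1.2, 6.2, 8.2 and 10.1 contradict that. The gap lies in the endpoint and its analysis, not in surveillance.

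Four other strong readings also go too far:

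- **The session certainly lies in neither window.** The protocol does not exclude the session day; it is silent.
- **Tolerability has no measure at all.** The questionnaire is planned, and Section 4 mentions it alongside safety and tolerability. What is missing is its place in 3.3.
- **Any subject with a seizure is withdrawn and lost.** A single short partial seizure only stops mapping for that day under 8.1(b), and 8.2 requires follow-up of events. Loss of the later diary after withdrawal is possible but not stated.
- **One induced seizure in 14 would be reported as 0 of 13.** The first is a proportion with an in-session seizure, the second a proportion with a diary increase. They are different quantities, and the second also assumes that the patient was withdrawn.

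It can also be said that 7.3 was written with the mapping comparison in mind. That is plausible, but the section does not limit itself to mapping and no other population is given.

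Finally, this is a small open-label feasibility study with no safety hypothesis. That limits the weight of the point. It does not remove it, because safety and tolerability is the stated secondary objective.

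**Conclusion.** The point holds as a defect of endpoint definition and analysis. As written, 3.3 cannot measure tolerability and does not clearly count a seizure during the session. Sections 7.2 and 7.3 leave the safety data already planned without an analysis or a suitable population.

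The size is modest. At the protocol's 5% rate there is about an even chance (51%) that at least one of 14 subjects has a mild effect, and any such effect other than a seizure would lie outside the endpoint. An in-session seizure is much less likely at the assumed rates (13% or 1.4%), but it is the event that the protocol itself ranks as most serious. Even a clean result would be weak: 0 of 14 is compatible with a true rate up to 19.3%.

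The figures rest on independence between subjects and on reading the 5% as a per-subject rate. The textual conclusion needs neither. No sample size or mapping result changes. The sponsor should make the correction, but the point does not threaten the primary comparison.

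**What to change.** 1. **Section 3.3.** Restate the endpoint as: (i) number of subjects with any seizure during nTMS or within 20 minutes after it; (ii) side-effects questionnaire results, as the number of subjects with each effect; (iii) new findings on the examination after nTMS compared with the one before; (iv) change in the 7-day diary seizure count, stating to which window the session day belongs.
2. **Sections 7.2 and 7.3.** Add a safety set of all subjects who receive any nTMS pulse, whether or not mapping is finished or DCS follows. Summarise each item by counts with exact confidence intervals. Keep the present 7.3 population for the mapping comparison.
3. **Sections 4.4.1 and 8.1.** State that a subject withdrawn because of an event at or after nTMS is still asked, if willing, for the questionnaire, the post-session examination and the 7-day post-nTMS diary. The stopping and withdrawal rules are not changed.

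The cost is small but not zero. Item (i) widens seizure recording slightly, since Section 1.4.1 now applies the 20-minute window only to generalized tonic clonic seizures. The analysis gains one short safety table, and the rare withdrawn subject is asked for a 7-day diary. The questionnaire, examinations and diaries are already scheduled. The questionnaire's content is not described, so severity should be tabulated only if the form grades it.

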4.1 Inclusion Criteria

1. 12-60 years of age
2. Planned neurosurgery involving implantation of intracranial subdural electrodes over the precentral gyrus

4.2 Exclusion Criteria

1. Inability to sign informed consent .
2. Hemiparesis worse than 4-5 on the side contra lateral to the planned implant
3. Inability to get an MRI, or MRI older than 2 years
4. Frequent (>1 per day) motor seizures
5. Prior neurosurgery
6. Metal in the head, including shrapnel
7. Implanted stimulation devices, including DBS, RNS, VNS, PPM
8. Pregnancy
9. Use of a medication known to increase the risk of seizures, including certain antipsychotics (clozapine), bronchodilators (aminophylline, theophylline), immunomodulatory agents (cyclosporine), and antibiotics (penicillins, cephalosporins, amphotericin, imipenem).

4.4 Early Withdrawal of Subjects

4.4.1 When and How to Withdraw Subjects

This study is expected to end after all participants have completed all visits, and all information has been collected. Under the following circumstances the subject's participation will be terminated by the investigator without regard to the participant's consent:

- The subject not able to attend the study visits required by the study.
- The subject fails to follow the study requirements.

- If a subject becomes pregnant.
- If a subject decides not to continue participation in the study (by choice)

5 Study Device

5.1 Description

Preoperative mapping was performed with **Magstim Rapid²** (Magstim) brain stimulation system. It delivers a biphasic TMS pulse from a figure-of-eight coil with an outer diameter of 70 mm. The system calculates the strength, location, and direction of the stimulating electric field in cortical tissue and takes the subject's head size and shape into account. The estimates of the induced electric field are based on a dynamic spherical model adjusted in real time and the physical parameters of stimulation.

Brainsight Navigation,(Rogue Resolutions) will provide the hardware and software environment to guide TMS application in a manner which is co-registered to the patient's MRI Brain. With combined use of the Magstim Rapid2 and Brainsight, the TMS coil can be navigated and positioned over a specified target location based upon the MRI Brain, thereby directing the stimulation in a spatially precise manner.

Neither the Magstim Rapid2 or Brainsight are FDA approved. However, the combination of **Magstim Rapid²** and **Brainsight NeuroNavigation** system is comparable to the Nextstim TMS system, which was FDA approved in 2009 for use in presurgical motor mapping (see attachment). Brainsight NeuroNavigation system is a non-significant risk device, as there it represents an imaging tool complementary to the TMS machines, and does not make contact with the patient.

5.2 Treatment Regimen

TMS with brief single pulse sequence and 3-4 seconds interval between pulses will be used in motor mapping in our study. The hand knob will be determined by free point to point stimulation as the location eliciting the largest MEP Reponses form the muscle interested, The resting motor threshold (rMT) was determined at the hand hotspot. rMT is defined as minimal stimulation intensity capable of generating an MEP in 50% of cases. Muscle representation areas relevant for clinical decisions were mapped with an intensity of 110% of rMT. Cortical muscle presentation areas were stimulated by an induced electric field orientated perpendicular to the central sulcus. The stimulation coil was hold tangential to the scalp. The tilt will be monitored on-line and adjusted so as to produce the strongest field strength in the cortex.

5.3 Method for Assigning Subjects to Treatment Groups

All subjects will be receive nTMS mapping in this open-label, phase 1 study , as well as standard procedures involved in the patient's clinical care involved in epilepsy surgery, including a preoperative MRI, functional mapping using DCS, and clinical followup.

5.4 Implantation of Study Device

TMS is a non-invasive form of neurostimulation. No surgical intervention or medication administration is needed before a TMS session.

5.5 Prior and Concomitant Therapy.

Epilepsy patients enrolled in this study will continue to receive standard of care for their management of epilepsy, and their medications will remain unchanged during phase 1 of participation (nTMS). However, patients will likely have their medications reduced while undergoing invasive monitoring for epilepsy surgery, according to standard clinical practice.

5.6 Receiving, Storage, Dispensing and Return

5.6.1 Receipt and storage of Study Device

The device has been obtained from [name] at the NYU Langone Medical center. [name]. The room is locked at the end of the day and can be open only by authorized personnel who have access to the door key. The TMS will be operated by qualified research staff personnel.

5.6.2 Dispensing and Return

The device will not be dispensed to subjects.

6. Study procedures

6.1 Baseline Visit: Informed Consent and baseline neurological visit (30 min)

This visit may happen in conjunction with a planned clinical visit. Patients will be educated on study design and eligibility requirements. If they are eligible and agree to study participation, they will be sign the informed consent. They will then be asked to maintain a 7 day seizure diary prior to the first study visit.

6.3 Visit 3: Post-operative clinic visit (30 min)

Patients will also be followed approximately 1 months after epilepsy surgery, in conjunction with their regularly scheduled clinical visits. A complete neurological exam will be performed and a questionnaire (Michigan Hand Outcomes Questionnaire) will be administered to detect any changes in motor strength and function after surgery.

7. Statistical Plan

7.1 Sample Size Determination

We estimate 10 subjects total necessary to detect a 50% difference between nTMS and DCS mapping, assuming alpha 0.05 and power 0.8. However, given the possibility of subject dropout, and the unknown nTMS side-effect profile and seizures we propose to add ~1/3 to total patient enrollment, and thus will enroll 14 patients. We plan to enroll at least 4 children ages 12-17 years, to assess for the validity of nTMS in a pediatric population, which is expected to benefit the most from this procedure.

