A neurostimulation technique, navigated transcranial magnetic stimulation (nTMS) is a potentially valuable tool for preoperative motor mapping. Previously there have been several studies to test the accuracy of TMS to DCS, and in comparison with other noninvasive modalities, including magnetoencephalography (MEG) and functional MRI (fMRI) (Najib 2011; Romero 2011, Tarapore 2012, Krieg 2012), suggesting that nTMS can have an extremely high degree of functional accuracy, identifying primary motor cortex within 2 mm of accuracy, and with a high positive and negative predictive value (Tarapore 2012).

A similar neuronavigated device, the integrated Nextstim device manufactured by Neurostar, was FDA approved for presurgical motor mapping in 2009 (Please see appendix). We are testing the Magstim Rapid² TMS coil and Brainsight Neuronavigation system (instead of the Nextstim) because the dual system allows co-registration to the patient's structural MRI, functional MRI(fMRI) or EEG. Furthermore,

¹ Electrical stimulation of the cerebral cortex will be conducted utilizing a NicoletOne Cortical Stimulator which delivers a constant current output. The stimulus parameters are set to a pulse width of 500 microseconds, pulse frequency of 50 Hertz and maximum train duration of 5 seconds. The stimulus current is manually controlled during the stimulation and ranged from 1 mA to 12 mA. Stimulation is applied to adjoining electrode pairs. Responses are confirmed with repeat stimulation and testing at the initial pair and with adjoining electrodes when necessary. Electrical stimulation is started at 1 mA and gradually increased in increments of 1-4 mA until a maximum of 12 mA was achieved or until after-discharges are seen or a functional response is observed. Positive and negative functional sites will be recorded.

the dual system is a more flexible system for other research use with other stimulation devices (such as transcranial direct current stimulation and simultaneous EEG recording) and robotic devices.

We propose an open-label feasibility study to test the accuracy of nTMS to the gold standard DCS, as well as to fMRI (an adjunctive presurgical planning tool), in determining both positive and negative motor sites, and correlate with clinical outcomes.

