2.1 Primary Objective

We propose a phase 1 clinical trial to examine the degree of concordance between neuronavigation guided TMS (nTMS) and direct cortical stimulation (DCS) in identifying hand motor cortex in adults and children undergoing epilepsy surgery.

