3.1.3 Follow-up clinical visit after the surgery

After epilepsy surgery patients will receive the standard care for post-operative patients which including close monitoring in ICU overnight. Patients will be transferred to the floor for further clinical evaluation before discharge. Clinical outcome will be evaluated in the post-operative clinic visit within 1 month after discharge. The value of a clinical follow up is to evaluate for any discrepancy between nTMS and DCS, to determine which modality better predicts functional outcome. Any seizure recurrence or neurological deficit will be recorded at the follow-up clinical visit.

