3.2 Primary Study Endpoints

The trial is designed to detect strength of spatial correlation between topographic maps of hand motor representation obtained through noninvasive nTMS compared to direct, extra-operative cortical stimulation obtained as part of usual clinical evaluation during epilepsy surgery, as measured by (a) average distance between positive motor mapping sites of DCS compared to nTMS and (b) degree of concordance between positive and negative motor mapping sites between DCS and nTMS, to generate positive and negative predictive values, and (c) average distance between positive motor functional sites of fMRI compared to nTMS.

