7.2 Statistical Methods

Maps of stimulation locations corresponding to hand and arm muscle groups will be formed. The distance between the averaged positive nTMS stimulation sites for each type of motor response (APB, ADM, etc) and the corresponding averaged DCS site will be calculated, according to co-registered 3D coordinates in MRI anatomical space. For DCS, the center of the electrode eliciting motor response with the lowest current will be defined; when stimulation of several electrodes elicited motor response with the same minimum current, the average ECS site of these electrode centers will be used instead. The weighted mean of the DCS map will also be calculated.

The distance between the averages of nTMS and DCS maps, between the site eliciting a motor response with a minimum current and between the average of the nTMS map and the weighted average of the ECS map will be calculated.

The localizations will be also compared in relation to the patients' gyral anatomy. If the nTMS localization and the electrodes eliciting positive motor response in ECS activated the same gyrus, the localizations will be defined as anatomically concordant.

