7.3 Subject Population(s) for Analysis

All subjects who complete the nTMS motor mapping session and later undergo direct cortical stimulation for functional mapping will be included in the analysis.

8. Safety and Adverse Events

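### The 80% power claimed in section 7.1 for a 50% difference belongs to no endpoint in 3.2 and no analysis in 7.2

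*Combined protocol and SAP*

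**What the plan says.** The whole basis for the base sample size is one sentence in 7.1: "We estimate 10 subjects total necessary to detect a 50% difference between nTMS and DCS mapping, assuming alpha 0.05 and power 0.8". The next sentence adds about one third for dropout and other losses, giving 14 enrolled.

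The rest of the document is about agreement:

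- **Objective (2.1):** "to examine the degree of concordance between neuronavigation guided TMS (nTMS) and direct cortical stimulation (DCS").
- **Endpoints (3.2):** (a) the average nTMS-DCS distance; (b) concordance of positive and negative sites, "to generate positive and negative predictive values, and (c) average distance between positive motor functional sites of fMRI compared to nTMS". The last of these, (c), does not involve DCS.
- **Analysis (7.2):** "The distance between the averaged positive nTMS stimulation sites for each type of motor response (APB, ADM, etc") and the matching averaged DCS site is calculated, along with variants based on the minimum-current site and on a weighted DCS average. When both methods point to the same gyrus, "the localizations will be defined as anatomically concordant".
- **Analysis set (7.3):** "All subjects who complete the nTMS motor mapping session and later undergo direct cortical stimulation" for functional mapping.

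Section 1.1 sets the scale of the study: "We propose an open-label feasibility study to test the accuracy of nTMS to the gold standard DCS".

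**The concern.** Power is a property of a specific test of a specific quantity. Section 7.1 quotes an alpha and a power but names no variable, scale, reference value, SD, sidedness or test, and 7.2 plans no test that could supply them. The sentence is the only source of the number 10, and the 14 follows from it. A reader can neither verify it nor connect it to any result the trial will report.

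What is at stake is interpretation. Section 7.2 asks for distances and a same-gyrus classification with no statement of uncertainty, and the power sentence suggests a level of assurance that the design does not supply. With about 10 patients, the uncertainty is the main thing a reader needs to see.

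**Working it through.** **1. Inputs.** From 7.1: 10 subjects, alpha 0.05, power 0.80, a 50% difference. Not given anywhere: the quantity, the SD, a base rate, the sidedness, the test, an agreement margin. Every SD below is an assumption.

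**2. Can the 50% difference be matched to an endpoint?**

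- *nTMS-DCS distance, 3.2(a).* This is already a comparison of the two maps: one non-negative number per patient or muscle. There is no separate nTMS value and DCS value to differ by 50%, and no reference distance is stated.
- *Site concordance with PPV and NPV, 3.2(b).* A 50% discordance rate is conceivable, but no null or target rate is given, and 7.2 contains no PPV or NPV calculation.
- *nTMS-fMRI distance, 3.2(c).* DCS is not involved.
- *The follow-up comparison in 3.1.3,* whose aim is "to evaluate for any discrepancy between nTMS and DCS, to determine which modality better predicts functional outcome". Section 7.2 contains no analysis of it.

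None fits.

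**3. Can the plan's 10 be reproduced?** Not from its stated inputs alone. Take a two-sided paired t-test as one possible reading. Power = P(|T| > t), where t is the 0.975 quantile on n − 1 degrees of freedom and T is noncentral t with noncentrality √n × difference / SD. With n = 10, t = 2.262 and a difference of 50 points:

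| Assumed SD | Noncentrality | Power at n = 10 | Smallest n for 80% |
|---|---|---|---|
| 40 | 3.162 × 1.25 = 3.95 | 93.9% | 8 |
| 50 | 3.162 × 1.00 = 3.16 | 80.3% | 10 |
| 75 | 3.162 × 0.667 = 2.11 | 46.9% | 20 |
| 100 | 3.162 × 0.50 = 1.58 | 29.3% | 34 |

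So 10 is obtained under this reading if the SD equals the difference. Other two-sided readings give other answers. Two independent proportions 50 points apart need 11 to 15 per group without continuity correction (22 to 30 in total). An exact McNemar test with 50% of patients discordant, all in one direction, needs 15. A correlation of 0.5 needs 30.

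The step from 10 to 14 is consistent: 10 × 4/3 = 13.3, rounded up to 14.

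**4. What can this sample size show about agreement?** Assume one value per patient.

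*Mean distance.* The 95% CI half-width is t × SD / √n:

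- n = 10: 2.262 / 3.162 = 0.715 SD
- n = 14: 2.160 / 3.742 = 0.577 SD

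*Gyral concordance.* When all n patients agree, the exact (Clopper-Pearson) 95% lower bound is 0.025^(1/n):

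- 10/10: 0.025^(1/10) = 69.2%
- 14/14: 0.025^(1/14) = 76.8%
- 9/10: the exact interval is 55.5% to 99.7%
- 4/4: 0.025^(1/4) = 39.8%, relevant to minors if exactly the minimum of 4 are enrolled and evaluable

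**5. Why a difference test suits the objective poorly.** If a paired test were run with 10 patients and the true difference were half an SD (the last row of the table), it would be non-significant 100 − 29.3 = 70.7% of the time. With no margin set, such a result would not show agreement.

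**The case against.** The strongest reply is that this is an open-label feasibility study of 14 patients, that a formal power calculation was never essential, and that 10 is a reasonable number. Much of that stands. The number is not shown to be wrong, at least one ordinary reading reproduces it, and nothing here requires more patients. The feasibility label could have excused the absence of a power calculation, but it does not support one that attaches to nothing.

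Two stronger readings are tempting, and the documents support neither.

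- A reader might infer that the investigators will take a non-significant difference as proof of concordance. No section says so, and since 7.2 plans no test, the plan as written produces no such result. Step 5 of the working is a caution only.
- A reader might infer that 7.2 will issue unsupported estimates for children. It plans no analysis by age. Sections 1.4.3 and 4 do say that including minors will establish validity, whereas 7.1 speaks only of assessing it. That is a difference in wording about why minors are included. The 39.8% bound applies only if exactly 4 take part and are evaluable; 4 is a minimum, and more children would raise it.

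It is also fair to say that a precision statement describes what 10 to 14 patients deliver without proving that this is enough. That stands, and the replacement text should call the sample size a feasibility number.

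**Conclusion.** The point holds as a defect of justification and reporting. The power stated in 7.1 corresponds to no endpoint in 3.2 and no analysis in 7.2, and it cannot be verified from the document. Under one reading it ranges from 93.9% to 29.3% as the assumed SD goes from 40 to 100 points. The documents do not show that 10 is too few, and they set no agreement margin against which adequacy could be judged.

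The precision figures assume one value per patient. The t-interval is a planning approximation, because distances cannot be negative and may be skewed. This should be fixed, but it is moderate in weight: enrolment and data collection are unaffected, and under 1.4.3 the nTMS maps are not given to the surgeons.

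**What to change.** Keep 14 enrolled.

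**Section 7.1.** Replace the power sentence with a precision statement for a quantity already in 7.2, for example:

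> The sample size is a feasibility number. For the distance between the averaged nTMS site and the averaged DCS site, taken as one value per patient (the mean over muscles), the 95% CI for the mean has half-width about 0.72 x SD with 10 evaluable patients and 0.58 x SD with 14. With one gyral-concordance result per patient, 10/10 concordant has an exact 95% lower bound of 69%, 9/10 gives 55.5-99.7%, and 14/14 has a lower bound of 77%.

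**Section 7.2.** Add a 95% CI for the mean of that same distance and an exact 95% CI for the proportion of patients with gyral concordance. State that the intervals describe agreement and do not test it, because no margin is set. The per-muscle and other distances stay as planned.

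**Optional.** In 1.4.3 and section 4, bring the wording about validity in minors into line with the more modest verb in 7.1.

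**Cost.** A few sentences of protocol text and two intervals. No extra patients, visits or data. The sponsor gives up a power claim, and the figures that replace it look less favourable.
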